## Section D: Purpose and Objectives

This study will examine the feasibility/acceptability of, and satisfaction with, a new intervention for family members of Veterans undergoing CBT for anxiety-based disorders. Adjunctive Family-CBT (AF-CBT) is framed within a family-systems approach, which addresses recovery of the Veteran within the context of the family unit rather than the patient as an individual. AF-CBT provides family members psychoeducation on anxiety and teaches skills that can be used to facilitate the recovery of Veterans who are in the process of completing treatment for anxiety.

A total of 47 Veterans and family member dyads (V/F dyad) will be recruited for this study. Phase 1 will recruit 12 V/F dyads for family members to receive AF-CBT while the Veteran undergoes CBT for anxiety. Each V/F dyad will participate in a post-treatment assessment that includes a semi-structured qualitative interview to gain a deeper understanding of their experience with the intervention and feedback on ways to refine the intervention. In this phase, AF-CBT will be delivered in three separate cohorts (approximately 4 V/F dyad in each cohort). The intervention will be refined using two adaptation frameworks (IM and FRAME) to guide the process, following completion of each cohort. Phase 2 of this study will recruit 35 additional V/F dyads to participate in the finalized version of AF-CBT.

Treatment feasibility, acceptability, and satisfaction will be evaluated via self-report assessment and qualitative interviews. The Family Accommodation Scale for Anxiety (FAS-A) will also be adapted for use with Veterans and administered at baseline and 1-month follow-up. The goal of this study is to further adapt and refine an adjunctive intervention for family members of Veterans who undergo CBT for anxiety. The long-term goal is to examine the effectiveness of AF-CBT as a therapeutic strategy to enhance the effectiveness of exposure-based treatments for anxiety for Veterans.

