## **Section F: Design/Procedure**

### **F1. Design**

Select one category that most adequately describes your research:

c) Pilot

Discuss the research design including but not limited to such issues as: probability of group assignment, potential for subject to be randomized to placebo group, use of control subjects, etc.

This study examines the feasibility and acceptability of, and satisfaction with, a new intervention for family members of Veterans undergoing CBT for anxiety disorders/PTSD. A total of 47 V/F dyads will be recruited. Phase I will focus on refining the AF-CBT intervention, and Phase II will deliver the finalized AF-CBT protocol to V/F dyads.

In phase 1, 12 V/F dyads will be recruited to refine the adapted AF-CBT intervention. Family members will receive AF-CBT while the Veteran undergoes iCBT for anxiety. The AF-CBT intervention will be delivered in

separate cohorts (approximately 4 V/F dyads in each cohort). During the 1-month assessment, information obtained from qualitative interviews with each cohort will subsequently be used to refine the intervention in an iterative process. In phase 2, 35 V/F dyads will be recruited and administered the finalized version of AF-CBT following the same treatment and assessment format. Qualitative interviews will focus on each V/F dyad's experience with the AF-CBT intervention and whether specific components of the intervention facilitated the Veteran's recovery process.

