## **F2. Procedure**

**Recruitment:** Veterans will be recruited through the Center for Innovative Treatment of Anxiety & Stress (CITRAS) at the Michael E. DeBakey VA Medical Center. CITRAS is an anxiety specialty clinic and receives direct referrals from clinics throughout the main hospital (e.g., General Mental Health Clinic, Post-Deployment Center, Primary Care Mental Health, PTSD Outpatient Clinic) and 11 community-based outpatient clinics (CBOCs). Flyers advertising the study will be posted throughout MEDVAMC and CBOCs, and the study will be advertised through electronic messaging boards throughout the hospital, posters, and VA approved social media outlets.

**Procedure:** Veterans expressing interest in the study will speak with a member of the study team who will provide information about the study. Veterans expressing interest in the study will be pre-screened with the Q-LES-Q-SF and BAI to determine if a moderate level of impairment in general functioning and anxiety are present (this data will not be included in research data set). If so, an appointment will be scheduled for interested Veterans and identified family members to complete a brief joint assessment, which will take about 2 hours. The Veteran will be scheduled for a separate appointment to complete a full baseline evaluation (where the Q-LES-Q-SF and BAI will be re-administered) approximately 2 weeks before receiving treatment. This appointment will last about 2.5 hours. The family member will start AF-CBT within 1-2 weeks of when the Veteran participates in anxiety treatment (delivered over 1 weekend). Approximately 2 weeks after the family member completes AF-CBT, the V/F dyad will meet with a study clinician for a conjoint (1.5 hour) booster session. The V/F dyad will be asked to complete a 1-month follow-up assessment, which will include a qualitative interview regarding their experience with the treatment (approximately 2.5 hours). It is anticipated that most participants will complete the study in approximately 4 months.

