Measures: (1) Community Reintegration of Injured Service Members (CRIS), a commonly used measure of community reintegration following deployment; (2) Beck Anxiety Inventory (BAI) assesses the severity of anxiety symptoms, minimizing those that overlap with depression; (3) DASS; (4) Quality of Life Enjoyment and Satisfaction Questionnaire- Short Form (Q-LES-Q-SF) is a brief, 16-item measure of subjective functioning and satisfaction across a range of life domains including work, leisure activities, social relationships, and physical health; (5) Saint Louis University Mental Status Exam (SLUMS) is an 11-item clinician-administered screening measure of cognitive impairment; (6) Anxiety Disorders Interview Schedule DSM-5 (ADIS-5) is a gold-standard semi-structured clinician interview used to assess for the presence of all anxiety disorders including PTSD. Modules examining the presence of psychosis, mood and substance abuse disorders are also included; (7) Demographic and Military Survey is a brief questionnaire we have used in previous studies that inquires about general demographic and military information. Veterans are asked about their periods of service, deployment dates, whether they seek healthcare outside of VA, and other information pertaining to their education and employment history; (8) Client Satisfaction Questionnaire-8 (CSQ-8) is an 8-item measure that assesses overall treatment satisfaction; (9) Family Accommodation Scale is a 16-item self-report measure of anxiety symptom accommodation during the past month; (10) Couples Satisfaction Index (CSI) assesses satisfaction in the relationship; (11) Revised Dyadic Adjustment Scale (RDAS) assesses several domains of relationship quality; (12) Modified Treatment Evaluation Inventory (MTEI) is a brief 9-item measure that uses a 5-point Likert scale to assess acceptability of treatment components; and (13) Inventory of Psychosocial Functioning (IPS) a measure that assesses functioning across different domains of life. The ADIS-5, SLUMS, Demographics Form will be given at baseline only and the CSQ and MTEI will given at 1-month follow-up only. The remaining measures will be administered at both time points.

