## **G2. Data Analysis**

Provide a description of your plan for data analysis. State the types of comparisons you plan (e.g. comparison of means, comparison of proportions, regressions, analysis of variance). Which is the PRIMARY comparison/analysis? How will the analyses proposed relate to the primary purposes of your study?

Specific Aim 1 involves the adaptation and refinement of AF-CBT through an iterative process, guided by two adaptation frameworks. Qualitative interviews involves a data-coding process will use conventional and directed content analysis/coding techniques. The data coding process will be divided into three steps: (1) Open Coding, in which [name] and the PI independently review the recordings to identify key emerging themes; (2) Top-Level Coding will be applied to the remaining interviews and differences will be resolved through consensus. New themes that emerge will be added to existing codes. (3) Sub Coding will be applied to further refine broad constructs represented by top-level codes into sub-categories.

Specific Aim 2 will examine the feasibility/acceptability of, and satisfaction with, AF-CBT. Feasibility will be the percentage of V/F dyads who agree to participate out of the number invited to participate (benchmark of 50%). Retention rate will be the percentage of family members who attend both sessions of AF-CBT including the booster session (benchmark of 70%). Acceptability will be measured using the MTEI, in which a score > 27 indicates the treatment was found to be acceptable. Satisfaction will be assessed through the CSQ-8, where a score > 25 indicates satisfaction.

Specific Aim 3 will assess the internal validity and test-retest reliability of the FAS-A adapted for Veterans and their family members. Cronbach's alpha will be used to test the internal consistency of the measure and Pearson's r will be used to calculate test-retest correlation of the measure administered at different time points.

An exploratory aim will use Pearson's r to examine the association between changes on the Family Accommodation Scale-Anxiety with changes on the CRIS45 and BAI measures.

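### Specific Aim 3 calls the baseline to 1-month correlation of the FAS-A test-retest reliability, although every dyad is due to be treated between the two administrations

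*Combined protocol and SAP*

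**What the plan says.** Section G2 sets Specific Aim 3 as an assessment of internal validity and "test-retest reliability of the FAS-A adapted for Veterans and their family members". Cronbach's alpha is to cover internal consistency, and Pearson's r "will be used to calculate test-retest correlation of the measure administered at different time points".

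G2 does not name the time points, but other sections leave only one pair. Section D says the scale "will also be adapted for use with Veterans and administered at baseline and 1-month follow-up". The Measures paragraph of F2 lists the baseline-only and follow-up-only instruments, and the Family Accommodation Scale is in neither list: "The remaining measures will be administered at both time points".

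Treatment falls between the two. The Veteran's full baseline is about 2 weeks before treatment. Under F1, "Family members will receive AF-CBT while the Veteran undergoes iCBT for anxiety", and Phase 2 dyads are "administered the finalized version of AF-CBT following the same treatment and assessment format". F2 adds that "The family member will start AF-CBT within 1-2 weeks of when the Veteran participates in anxiety treatment", with a conjoint booster about 2 weeks after AF-CBT and then the 1-month follow-up.

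The exploratory aim in G2 uses the same two FAS-A scores to "examine the association between changes on the Family Accommodation Scale-Anxiety with changes on the CRIS45 and BAI measures".

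**The concern.** A test-retest correlation estimates reliability only if the respondents' true scores keep their relative positions between the two occasions. Here the interval contains an intervention aimed at the construct being measured: the Treatments paragraph of F2 says AF-CBT covers the role of accommodation and teaches alternatives to it. If some dyads reduce accommodation more than others, the two scores will disagree even when the scale measures perfectly.

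G2 then puts the same score differences to two uses. Aim 3 counts disagreement between occasions against the scale's reliability. The exploratory aim takes the differences as a change variable worth relating to change in reintegration and anxiety.

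What is at stake is the description of the adapted scale. A sound instrument could be reported as having weak test-retest reliability, and Section I says this pilot will inform a larger trial.

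**Working it through.** **Stated figure.** G2 gives no target r, precision or threshold for Aim 3, so there is no plan figure to reproduce. The check has two parts: whether the design can support the label, and how far r could move.

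**Design.**
- FAS-A occasions: two (Section D; F2, Measures).
- Planned between them: iTCBT for the Veteran, AF-CBT for the family member, booster for the dyad (F2).
- Untreated comparison group: none. Both phases use the same format (F1).
- Second pre-treatment FAS-A: none described. The only measures repeated before treatment are the Q-LES-Q-SF and BAI, and their pre-screen values are kept out of the research data set (F2).

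**General result.** Under classical test theory with uncorrelated errors,

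r = corr(T1, T2) × √(rel1 × rel2),

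where T1 and T2 are the true scores and rel1 and rel2 the reliabilities at the two occasions. If every dyad changes by the same amount, corr(T1, T2) = 1 and r is unaffected. If true change differs between dyads other than as a linear function of baseline, corr(T1, T2) falls below 1.

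**Illustration. All inputs are assumptions, because the documents give no FAS-A SD, reliability or expected change.** Let X1 = T + e1 and X2 = T − D + e2, with Var(X1) = 1, reliability R = Var(T) = 0.85 and equal error variances. Let k = SD(D)/SD(T) and ρ = corr(T, D), where D is the true reduction in accommodation. Then

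V = SD2²/SD1² = 1 + R·k² − 2·ρ·k·R, and r = R(1 − ρ·k)/√V.

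Worked case, ρ = 0 and k = 0.7: V = 1 + 0.85 × 0.49 = 1.4165, √V = 1.190, r = 0.85/1.190 = 0.714.

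Worked case, ρ = 0.5 and k = 1.0: V = 1 + 0.85 − 0.85 = 1.00, r = 0.85 × 0.5/1.00 = 0.425.

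| k | r, ρ = 0 | SD ratio, ρ = 0 | r, ρ = 0.5 | SD ratio, ρ = 0.5 |
|---|---|---|---|---|
| 0.2 | 0.84 | 1.02 | 0.82 | 0.93 |
| 0.4 | 0.80 | 1.07 | 0.76 | 0.89 |
| 0.7 | 0.71 | 1.19 | 0.61 | 0.91 |
| 1.0 | 0.62 | 1.36 | 0.43 | 1.00 |

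With ρ = 0, r × SD ratio returns 0.85. With ρ = 0.5 it does not, and in the last row an unchanged SD goes with a shortfall of 0.85 − 0.425 = 0.425.

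**Cases that do not lower r.**
- True and error parts shrinking in proportion: r stays at 0.85.
- True scores fanning out by a factor of 1.3, errors unchanged: r = 1.3 × 0.85/√(1.69 × 0.85 + 0.15) = 0.877.
- Errors correlated at q = 0.3 (for example, remembered answers), ρ = 0: r = (0.85 + 0.3 × 0.15)/√(1 + 0.85·k²), which is 0.895 at k = 0 and 0.752 at k = 0.7.

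**Precision.** The Fisher-z 95% CI is tanh(atanh r ± 1.96/√(n − 3)). G1 allows 20% attrition on 35 Phase 2 dyads, so n = 35 × 0.8 = 28. If Phase 1 is included and the same loss is assumed, 47 × 0.8 = 37.6, about 38.

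| r | n = 28 | n = 38 |
|---|---|---|
| 0.80 | 0.61 to 0.90 | 0.65 to 0.89 |
| 0.71 | 0.46 to 0.86 | 0.50 to 0.84 |

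**Can the SDs separate error from change?** Only partly. With ρ = 0, an r of 0.714 fits reliability 0.714 with SD ratio 1.00, and also reliability 0.90 with SD ratio 1.26. In 20,000 simulated samples of 28, the central 95% of observed SD ratios was 0.76 to 1.31 in the first case and 0.96 to 1.67 in the second, so the two overlap widely.

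**The case against.** The strongest case against is about importance. This is a single-arm pilot whose purpose is feasibility, acceptability and satisfaction. No decision rule uses r, and alpha and Aims 1 and 2 are untouched. Size and direction are assumed: if true change varies little (k = 0.2), r is 0.84 or 0.82 against 0.85, and even the 0.05 shortfall at k = 0.4 with ρ = 0 is smaller than sampling error. A k of 1.0 is a lot to expect from two 2-hour sessions and a booster alongside iTCBT. Fanning-out or correlated errors would raise r. G2 also nowhere says that FAS-A change is real; it only correlates change scores.

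These points stand as limits on the consequence. They do not rescue the label, which depends on none of the assumed values: an interval filled with treatment aimed at the construct is not a retest interval. Nothing in the plan makes response uniform, and the booster is meant to tailor components to each dyad.

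A further objection is that keeping r with a caveat would be lighter. Relabelling is hardly heavier, and it avoids reporting a reliability figure that the caveat would have to disown.

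**Conclusion.** The concern holds. The only FAS-A pair available is pre- and post-treatment, so G2 as written would report a correlation that mixes measurement error with treatment response as the scale's test-retest reliability. That conclusion rests on the documents alone. It does take the 1-month follow-up to come after AF-CBT and the booster; F2 gives that order without stating what the month is counted from.

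The size is conditional. With reliability assumed at 0.85, r ranges from 0.84 down to 0.43 over the cases tabulated, and can exceed 0.85 if errors are correlated or true scores fan out. Understatement is the usual direction. A low r should not by itself be read as poor reliability. The effect is limited to one component of Aim 3, so this should be fixed but does not threaten the trial's main aims.

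**What to change.** **Core change, G2 only.** Describe the baseline to 1-month Pearson's r as a pre-post correlation, and report it with the SD at each occasion, the number of pairs and a 95% CI. State whether Phase 1 dyads are included. Do not report it as test-retest reliability. Keep Cronbach's alpha as the reliability evidence for Aim 3, noting that alpha does not capture occasion-specific error. This needs no new data. Its cost is that Aim 3 no longer has a test-retest estimate.

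**Optional, only if a test-retest estimate is wanted.** Give the FAS-A a second time before iTCBT or AF-CBT starts, and estimate reliability from the two pre-treatment scores, for example with an ICC and 95% CI. F2 does not say who completes the scale, so name the respondent there. The cost is one extra 16-item form per respondent and an edit to F2. The weakness is that the scale asks about the past month. Two administrations close together would have overlapping recall windows, which may inflate agreement and should be stated. Windows that do not overlap need about a month between administrations, which may not fit the F2 schedule.

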Recent research shows that interpersonal factors between a patient with anxiety and a family member may also function to maintain anxiety symptoms through a process known as accommodation. This occurs when family members adjust their own behaviors to help reduce the distress experienced by their loved one. This may take the form of the family member providing constant reassurance to the patient, using distraction, serving as a safety object by accompanying the patient outside of their comfort zones, warning others how to behave around the patient, and assuming more responsibilities typically handled by the patient. Although well-intentioned, accommodation behaviors by family members are detrimental and directly undermine the effectiveness of CBT approaches by facilitating further avoidance for the patient. Accommodation behaviors are associated with increased symptom severity and functional impairment. Over time, this pattern of responding becomes strenuous and exhausting to the family member and can deteriorate the relationship with the loved one. Thus, when a member of the family has mental illness, it impacts the family as a system by disrupting the equilibrium within that unit. In these instances, family members adjust patterns of how they respond and interact with the individual to restore balance to the family unit.

Despite this knowledge, the primary focus of most current evidence-based CBT approaches for anxiety continue to focus exclusively on treating the symptomatic individual. Only recently have researchers begun investigating brief interventions to target decreasing accommodation behaviors in family members of adult patients. Such interventions provide psychoeducation on how anxiety is maintained and teach family members new skills that will facilitate the patient's recovery from anxiety. These studies, along with results obtained from pediatric samples show that addressing accommodation behaviors in treatment is associated with reduced symptom severity, increased treatment response, satisfaction, and engagement by family, and improved remission rates.

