**Inclusion Criteria:**

(1) Veteran at least 18 years old; (2) current diagnosis of at least one anxiety-based disorder: PTSD, PD, SAD, GAD, or Other Specified Anxiety Disorder (based on ADIS-5); (3) moderate-to-poor life enjoyment and satisfaction as indicated by a score of 47 or lower on the Q-LES-Q-SF (4) BAI score of 16 (moderate anxiety) or higher; (5) stable on psychotropic medication for 4 weeks before study participation; and (6) has a family member willing to participate in the study. The identified family member must be an adult over the age of 18 years who either lives with the Veteran or has frequent contact (>3 days/week) and can commit the time to attend the AF-CBT intervention.

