**Assessments:** Veterans will undergo two assessments (baseline & 1-month follow-up). The baseline evaluation will include a structured diagnostic interview (ADIS-5) and psychological screening measures to determine general emotional functioning and the presence of specific psychiatric disorders. All assessments will be supervised by a licensed psychologist. Veterans will be informed that study staff will need to access their medical records periodically to track relevant psychiatric and medical information. Protected health information that will be collected from Veterans in this study include: name, address, telephone numbers, dates of appointments related to the study, last four digits of social security number, and voice recordings. Demographic information, medications prescribed, and dates of mental health treatment appointments will also be collected. VA Quality Assurance and BCM IRB personnel responsible for providing general oversight of this study may also have access to research data. Study data regarding individual information that is not in the patient's medical record will remain confidential and inaccessible to other agencies. Family members will also be asked to complete a few brief measures at baseline and 1-month follow-up time points.

**Qualitative Interviews:** All V/F dyads who complete AF-CBT will be invited to participate in a qualitative interview following completion of AF-CBT. The purpose of the interview is to obtain V/F dyads' feedback about AF-CBT.

Collection and analysis of qualitative data will be overseen by Co-I, [name], and interviews will be conducted using a semi-structured interview guide (attachment in Section S) by [name] (consultant). All interviews will be digitally audio-recorded using a microphone linked directly to a VA networked computer. De-identified audio recordings of the interviews will be saved to the MEDVAMC Research folder on the S Drive: Research-Data/[name] Lab. Lighthouse for the Blind will transcribe the audio recordings by accessing the research folder on the S Drive through their contractor PIV card or through receiving files via encrypted e-mail. Transcriptions will be saved to the research folder.

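### Does correlating unadjusted changes in accommodation and anxiety create a false association through shared baseline severity?

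*Combined protocol and SAP*

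**What the plan says.** Section G2 (Data Analysis) lists three specific aims and then one further, exploratory aim, which will "use Pearson's r to examine the association between changes on the Family Accommodation Scale-Anxiety with changes on the CRIS45 and BAI measures". No covariate, regression model or partial correlation is named for it, and no significance level, hypothesis or decision rule.

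Change is not defined, but section F2 leaves little doubt. On timing it says "Veterans will undergo two assessments (baseline & 1-month follow-up)", and of the scales not confined to one visit it says "The remaining measures will be administered at both time points". One difference per dyad, follow-up minus baseline, is the natural reading.

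Two other statements bear on the point. Section C says "Accommodation behaviors are associated with increased symptom severity and functional impairment", giving a direction but no coefficient. The inclusion criteria require a "BAI score of 16 (moderate anxiety) or higher". Section F2 adds that the pre-screening values stay out of the research data and that there is a full baseline visit "where the Q-LES-Q-SF and BAI will be re-administered".

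**The concern.** A change score usually correlates negatively with its own baseline. If accommodation and anxiety are already correlated at entry, as section C leads one to expect, a dyad that is high on both might be expected to fall on both simply by returning toward average. An unadjusted r would count that as association. The BAI entry threshold seems to make it worse, because it selects Veterans with high scores. All the baseline scores are collected, so adjustment would cost nothing in data.

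The stake would be a bias in the hoped-for direction. This is the only planned quantitative analysis of whether less accommodation goes with Veteran improvement, and there is no control arm that could expose an artefact.

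**Working it through.** **Inputs.** From the documents: 47 dyads in all (section F1: "A total of 47 V/F dyads will be recruited"), 35 of them in Phase 2, and 20% attrition (section G1). Evaluable dyads: 35 × 0.80 = 28 in Phase 2, or 47 × 0.80 = 37.6, say 37, overall. The plan states no figure for this analysis, so there is none to reproduce. Assumed throughout: the baseline correlation between the two scales (ρ), the correlation of each scale with itself from baseline to follow-up (s), unit variances, and a two-sided 5% test, which the plan does not itself specify.

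**Structure 1: drift from the observed baseline.** Each follow-up equals s × baseline plus an independent residual with variance 1 − s².

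- Variance of each change: (1 − s)² + (1 − s²) = 2(1 − s).
- Covariance of the two changes: ρ(1 − s)².
- Correlation of the changes: **ρ(1 − s)/2**.

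| ρ, s | Formula | Simulated mean r (n = 28) | Positive at 5% |
|---|---|---|---|
| 0.3, 0.5 | 0.075 | 0.072 | 6.6% |
| 0.3, 0.3 | 0.105 | 0.100 | 7.4% |
| 0.5, 0.5 | 0.125 | 0.124 | 9.7% |
| 0.5, 0.3 | 0.175 | 0.173 | 13.6% |

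Here the partial correlation given both baselines averages within 0.004 of zero, with 4.8 to 6.0% positive. Under this structure the concern is right. The effect shrinks as stability rises: at ρ = 0.5 and s = 0.7 it is 0.5 × 0.3/2 = 0.075.

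**Structure 2: correlated stable levels plus independent error at each visit.** This is ordinary regression to the mean through measurement error. Each change still correlates negatively with its own baseline, but every cross-scale covariance, within or between visits, equals ρ.

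- Covariance of the two changes: ρ − ρ − ρ + ρ = 0. The planned r is centred on zero.
- Residual covariance of the two follow-ups given both baselines: ρ(1 − s)²/(1 − ρ²).
- Residual variance of each: (1 − s)(1 + s − 2ρ²)/(1 − ρ²).
- Partial correlation: **ρ(1 − s)/(1 + s − 2ρ²)**.

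| ρ, s | Partial r, formula | Simulated planned r, positive | Simulated partial r, positive |
|---|---|---|---|
| 0.3, 0.5 | 0.15/1.32 = 0.114 | 0.00, 4.7% | 0.116, 8.9% |
| 0.3, 0.3 | 0.21/1.12 = 0.188 | 0.00, 5.1% | 0.177, 14.6% |
| 0.5, 0.5 | 0.25/1.00 = 0.250 | 0.00, 5.0% | 0.245, 23.6% |

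The pair (0.5, 0.3) cannot occur here, because ρ cannot exceed s. A shared stable component cancels in each difference. Adjusting for error-prone baselines removes it only in part, and the remainder appears as association between changes that are unrelated.

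**The BAI threshold.** Under structure 1, cutting the BAI baseline at −0.5 SD (assumed) restricts its range and lowers the induced r from 0.125 to 0.066 at (0.5, 0.5), and from 0.169 to 0.093 at (0.5, 0.3). Under structure 2 the planned r stays at zero, since the FAS-A errors are independent of everything the selection uses. The threshold does not aggravate the problem under either structure.

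**Scale.** By Fisher's z, the 95% limits around r = 0 are tanh(1.96/√25) = ±0.37 at n = 28 and tanh(1.96/√34) = ±0.32 at n = 37. Every value in the first table lies well inside them.

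**The case for a change.** The strongest reply is that structure 2 is too kind to the plan. At (0.3, 0.3) and (0.5, 0.5) it makes accommodation and anxiety a single underlying quantity, since ρ/s = 1, and it has nobody respond although both dyad members receive an intervention. Take instead two distinct true scores correlated 0.3 to 0.5, reliability of 0.8 to 0.9, and true scores that shrink toward the mean by a fraction k (all assumed). The planned r is then about 0.00 at k = 0, 0.05 to 0.17 at k = 0.4, and 0.09 to 0.27 at k = 0.6. The partial correlation never exceeds 0.05. If sicker dyads improve more, adjustment is the better choice.

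That part stands, as a conditional statement. It does not establish a defect. At (0.3, 0.5) the two stable levels are distinct, correlated 0.3/0.5 = 0.6, and the partial correlation is still wrong by about 0.11 while the planned r is not. Which method errs depends on how far response depends on baseline and on how reliable the adapted FAS-A is. The documents give neither, and the FAS-A's reliability is itself under study in Specific Aim 3.

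Low precision does not excuse bias, so the ±0.37 limits are not an answer alone. They do show how little the point could alter what a reader takes from a single-arm pilot. Section F1 also has the interviews ask whether components of the intervention helped the Veteran recover, so the correlation is not the only evidence on that question. Defining change and reporting an adjusted analysis alongside would be useful detail; leaving it out is not an error.

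**Conclusion.** The concern does not hold. Correlated baselines do not by themselves make unrelated changes correlate; the changes must also depend on their own observed baselines. With that dependence the planned r is inflated by roughly 0.07 to 0.17 for 28 dyads. Without it, under plain measurement error, the planned r is unbiased and the baseline-adjusted replacement is inflated by roughly 0.12 to 0.25. All these sizes rest on assumed correlations of 0.3 to 0.5, and the documents supply nothing that favours one structure.

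The plan also sets itself a descriptive question, whether the changes go together, and an unadjusted r estimates exactly that. It attaches no causal or mediating reading, no test and no go/no-go rule to the answer. Choosing change scores over baseline adjustment for such an exploratory estimate is a judgement on which competent statisticians differ, and the plan's choice is defensible.
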